7. RESEARCH QUESTION AND OBJECTIVE(S)

The primary purpose of this multinational, multisite, non-interventional study is to understand the real-world use of belantamab mafodotin by characterizing RRMM patients treated with belantamab mafodotin in routine clinical practice in Europe. In addition, this study will provide further evidence on belantamab mafodotin's risk-benefit profile by collecting safety and effectiveness data. This information will be used to inform current and future clinical practice. No formal hypotheses are being tested in this study.

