7.2. Secondary Objectives

The **key secondary objective** of this study is to characterize patients who experience ocular adverse events (AEs) that have been associated with belantamab mafodotin treatment (ocular Adverse Events of Special Interest [AESIs]) (overall and by line of treatment) in terms of:

- Belantamab mafodotin treatment received (i.e., dose and duration)
- Ophthalmic disease history
- Ocular AESI type, duration and severity
- The frequency and timing of ophthalmic monitoring visits relative to belantamab mafodotin administration (for each cycle; overall and by line of treatment, occurrence of ocular AESIs as well as treatment dose and frequency).

Other secondary objectives are the following (overall and by line of treatment):

- Assess the incidence of ocular AESIs and their impact on treatment discontinuation, interruption/delay, or dose modifications (additionally evaluated by comorbidity, ocular AESI type and severity as well as treatment dose and frequency)
- Evaluate persistence and adherence with belantamab mafodotin
- Describe reasons for treatment discontinuation
- Describe the duration and reasons of treatment interruptions/delays, or dose modifications
- Evaluate effectiveness in terms of disease response to treatment, DoR, duration of treatment (DoT), real-world progression-free survival (rwPFS) and OS.

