8.2.3. EU Setting Considerations

8.3. Variables

8.3.1. Definitions

[figure not shown]
The following definitions apply to the different timings of data collection (see [Figure 2](#)):

- **Index date** is defined as the time of the first (non-missing) dose of belantamab mafodotin.
- **The baseline period** for data collection is defined as the time from the initial MM diagnosis until the index date (the first dose of belantamab mafodotin).
- **The post-index period** spans from the index date until the end of follow-up at 15 months, study discontinuation for any reason, informed consent withdrawal or death; whichever comes first.
- **The post-index treatment period** is defined as the duration of the belantamab mafodotin line of treatment (DoT). This spans from the index date until the confirmed decision date of permanent discontinuation of belantamab mafodotin treatment, the

confirmed date of a new line of treatment or the date of the end of follow-up at 15 months, study discontinuation for any reason, informed consent withdrawal or death; whichever comes first.

- **The study period** spans from the time from the initial MM diagnosis until the end of follow-up at 15 months, study discontinuation for any reason, informed consent withdrawal or death; whichever comes first.
- **Active treatment exposure periods** are defined as the time that belantamab mafodotin is considered to have a treatment effect during the post-index treatment period. This period includes all doses occurring within 70 days of the previous dose (belantamab mafodotin's half-life) from the date of the first belantamab mafodotin dose of that sequence to the date of the last dose +70 days or the date of the end of the post-index treatment period; whichever comes first.

Figure 2 Timings of Data Collection

[figure not shown]
Abbreviations: MM=multiple myeloma.

The following definitions apply to collection of treatment data:

- **Line of treatment** is defined as one or more completed cycles of a single agent, a regimen consisting of a combination of several drugs, or a planned sequential therapy of various regimens (Rajkumar, 2015).
- **A treatment cycle** is defined as the belantamab mafodotin label-approved dosing interval, which is 21 days (with a real-world scheduling grace period of +7 days).
- **Treatment discontinuation** is defined as a recorded clinician decision (with an associated decision date) to permanently discontinue belantamab mafodotin treatment.

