- **Treatment interruption** is defined as withholding ≥ 1 belantamab mafodotin dose for any reason without a confirmed clinician decision to permanently discontinue treatment or initiate a new line of treatment. The time interval between doses will be >2 treatment cycles (+ 7-day grace periods).
- **Treatment delay** is defined as a delay (intentionally or unintentionally) in receiving belantamab mafodotin without skipping a dose. The time interval between doses will be >1 treatment cycle (+ a 7-day grace period) and <2 treatment cycles.

Figure 3 shows examples of treatment sequences that patients might undergo during the 15-month follow-up period.

Figure 3 Examples of treatment sequences during the post-index period

The following definitions apply to derived outcomes for statistical analyses:

- ORR is defined as the proportion of patients with a best response (sCR, CR, VGPR or partial response [PR]) during the study period evaluated by a responsible physician based on International Myeloma Working Group [IMWG] criteria if feasible or to local standard practice
- OS is defined as the time in months from the start of belantamab mafodotin treatment to the date of death due to any cause
- rwPFS is defined as the time in months from the start of belantamab mafodotin treatment to the date of the first documented disease progression or death, whichever occurs first
- DoR is defined as the time from the first documented evidence of PR or better until the earliest date of progressive disease (PD) or death among patients who achieved a response

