8.3.3. Belantamab Mafodotin Treatment

Belantamab mafodotin treatment data to be collected during follow-up from standard of care visits are shown in [Table 3](#). Data will be collected from the time of the first belantamab mafodotin dose until permanent discontinuation of belantamab mafodotin treatment, the end of follow-up at 15 months, study discontinuation for any reason, informed consent withdrawal or death; whichever comes first.

Table 3 Belantamab mafodotin treatment

Variable	Definition	Timing
Date(s) of Administration	Date of each administration	Index date and post-index treatment period
Dose	Continuous variable: prescribed and administered doses	Index date and post-index treatment period
Treatment status change	Categorical variable: prospectively captured or derived retrospectively 
 • Dose modification • Treatment interruption / delay • Discontinued 	Post-index treatment period
Primary reason dose modification	Categorical variable: 
 • Any AE • Other 	Post-index treatment period
Primary reason treatment interruption/delay	Categorical variable: 
 • Any AE • Patient decision unrelated to AEs • Other 	Post-index treatment period
Primary reason treatment discontinuation	Categorical variable: 
 • Disease progression • Any AE • Patient decision unrelated to AEs • End of treatment • Death (unrelated to therapy) • Other 	Post-index treatment period
Concomitant Medications	Categorical variable: type of concomitant medication* Continuous variable: dose at index date for each concomitant medication	Index date and post-index treatment period

Abbreviations: AE=adverse event.

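### The interval limits for treatment delay and interruption do not meet, and a single withheld dose resumed at day 42 fits neither full definition

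*Protocol*

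**What the plan says.** Protocol 8.3.1 defines the treatment cycle as the labelled dosing interval, "which is 21 days (with a real-world scheduling grace period of +7 days").

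The two definitions at issue each combine a verbal test with an interval test:

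- **Interruption.** The verbal test is "withholding ≥ 1 belantamab mafodotin dose for any reason", with no decision to stop permanently or start a new line. The interval test is "The time interval between doses will be >2 treatment cycles (+ 7-day grace periods").
- **Delay.** The verbal test is a late dose "in receiving belantamab mafodotin without skipping a dose". The interval test is "The time interval between doses will be >1 treatment cycle (+ a 7-day grace period) and <2 treatment cycles".

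Table 3 (8.3.3) describes how a change in treatment status is obtained: "Categorical variable: prospectively captured or derived retrospectively". It also collects the date of every administration. One of the other secondary objectives in 7.2 is "Describe the duration and reasons of treatment interruptions/delays, or dose modifications". Section 8.7.2.4 plans counts, proportions, Kaplan-Meier times and durations for interruptions and delays due to an ocular AESI. Section 8.7.2.5 lists a subgroup contrasting interrupted with continuous dosing.

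**The concern.** Two definitions that together describe late dosing should meet at one boundary. Here grace appears on one side of the boundary and not on the other, so a band of intervals may belong to neither category. The band begins at 42 days, which is what results when one dose is withheld and treatment resumes at the next three-weekly visit. Sections 5, 8.3.7 and 8.9.5 all assume visits about every three weeks.

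At stake is how often, and for how long, treatment is interrupted or delayed, including because of ocular AESIs. If a one-dose hold has no clear category, these summaries depend on whether the person or program assigning the status followed the wording or the interval.

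**Working it through.** **Inputs, all from 8.3.1.** Cycle 21 days; grace 7 days; delay above 1 cycle plus 7 days and below 2 cycles; interruption above 2 cycles plus 7-day grace periods (plural, number not stated).

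**Literal limits in days.**

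- Delay, lower limit: 21 + 7 = 28, so more than 28.
- Delay, upper limit: 2 × 21 = 42, so less than 42. In whole days, 29 to 41.
- Interruption with one grace period: 2 × 21 + 7 = 49, so day 50 onward.
- Interruption with one grace period per cycle: 2 × 21 + 2 × 7 = 56, so day 57 onward.
- Neither: 42 to 49 (49 − 42 + 1 = 8 whole-day values) or 42 to 56 (56 − 42 + 1 = 15 values).

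**Other readings.** Because the wording on grace is ambiguous, every whole-day interval from 1 to 99 was classified under five readings.

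| Reading | Delay | Interruption | Late but in neither |
|---|---|---|---|
| A. 21-day cycle, one grace period on interruption | 29–41 | 50 or more | 42–49 |
| B. 21-day cycle, one grace period per cycle on interruption | 29–41 | 57 or more | 42–56 |
| C. Grace built into the cycle (28 days), parentheses only a reminder | 29–55 | 57 or more | 56 |
| D. 21-day cycle, no grace on interruption | 29–41 | 43 or more | 42 |
| E. Grace built into the cycle and added again | 36–55 | 71 or more | 56–70 |

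A and B follow the printed text most directly. C is the most favourable reading that keeps the stated grace. D ignores grace that the bullet states. E counts it twice. No reading gives an overlap, and none closes the gap completely.

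**One withheld dose, resumed on schedule: 2 × 21 = 42 days.**

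- Interruption: the verbal test is met, since one dose was withheld. The interval test fails under all five readings, because 42 is not above 49, 56, 56, 42 or 70.
- Delay: the interval test fails under A, B and D, because 42 is not below 42. It is met under C and E, but the verbal test fails because a dose was skipped.

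So this hold meets the full criteria of neither definition under any reading.

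**The same hold, resumed later.** If resumed within a 7-day grace (42 to 49 days), no day qualifies as an interruption under A, B, C or E; under D, days 43 to 49 do. If resumed later still, it counts as an interruption from day 50 under A and from day 57 under B.

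**Effect by route of data capture.** Suppose that status derived retrospectively is derived from administration dates. Under A or B, a 42-day hold then drops out of interruptions and delays alike, so a combined category loses it too. Under C, a program using dates alone would place it with the delays, against the delay wording. A site recording status as it happens can call it an interruption on the wording.

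**The case against.** The strongest reply is that the practical effect is limited, and most of that reply stands.

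- **Capture by sites.** Enrolment is prospective by default. Patients already dosed are invited only if recruitment is slow, and 8.5 expects them to be few. For prospective patients, Table 3 lets the site record the status, and the verbal rule allows it to record a one-dose hold. A reader might infer that a single withheld dose is never counted; the document does not support that. Loss is certain only where the interval decides.
- **A separate data item.** Table 5 records interruption or delay as an action taken for each ocular AESI, and Table 3 records the primary reason. Neither is stated to depend on the dosing interval. A reader might infer that the effect of ocular AESIs on treatment is necessarily understated. That does not follow, because these items can capture the hold.
- **Combined reporting.** The objectives, tables and analyses mostly treat interruption and delay together, so the split between them matters less. The gap remains, because under the literal readings it lies outside both.
- **A 28-day cycle.** This reading is reasonable and reduces the numeric gap to day 56. It leaves the one-dose hold in conflict with the delay wording.
- **Continuous treatment.** A reader might infer that affected patients would be classed as continuously treated. The protocol does not define that group, and leaves the rules for the subgroup to the SAP, which is not at hand.
- **Recoverability.** Every administration date is collected, so intervals can be reclassified at analysis.

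Figure 3, which gives example treatment sequences, is not shown and may clarify intent. It would not change the printed limits. Nor is this simply a matter for the SAP: the protocol fixes the limits itself, and a SAP that closed the gap would have to depart from them.

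**Conclusion.** The inconsistency is real and should be fixed. On the literal 21-day cycle, 42 to 49 or 42 to 56 days meets neither interval rule; with grace built into the cycle, only day 56 is numerically unassigned. Under either reading, one withheld dose resumed at day 42 satisfies the interruption wording, fails the interruption interval, and cannot be a delay.

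The consequence is classification that can differ between sites and between recorded and date-derived status, with such holds lost where dates alone are used under the literal limits. This rests on three-weekly visits, as the protocol assumes, and on retrospective derivation using administration dates.

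The effect is confined to secondary descriptive outcomes. The primary objective does not use these definitions, and 7 states: "No formal hypotheses are being tested in this study". The number of intervals affected cannot be known from the document. These limits make it a correction worth making before status is classified, not a threat to the study's main purpose.

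**What to change.** Amend the two bullets in 8.3.1 as a matter of outcome classification only:

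1. State one day as both the upper bound of delay and the lower bound of interruption, with one of the two inequalities including that day.
2. State whether grace applies to that bound and, if so, how many grace periods.
3. Make the bound consistent with both verbal tests, or say which test prevails when wording and interval disagree.
4. Apply the same rule to status recorded prospectively and status derived from dates.

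The choice of day is the sponsor's, and each choice has a price. A bound at 42 days agrees with the withheld-dose wording but removes the stated grace, so a dose given at day 43 with none deliberately withheld would count as an interruption. A later bound keeps the grace but places a 42-day one-dose hold among the delays, so the delay wording would have to change.

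The cost is an edit to two definitions and the matching derivation. No new data are needed, because administration dates are already collected. Some intervals now unclassified will be counted as delays or interruptions, so those totals may rise.

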As shown in [Figure 1](#), eligible RRMM patients from sites who received their first belantamab mafodotin dose before study enrolment will only be invited for study participation if this is deemed necessary based on the enrolment rate in the EU.

Belantamab mafodotin use and ophthalmic monitoring data will be collected while patients are on treatment. Safety and effectiveness data will be collected regardless of whether patients are on treatment or have discontinued treatment during follow-up.

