8.3.6. Effectiveness

Table 6 shows the effectiveness data to be collected during the study period from the time of the first belantamab mafodotin dose until the end of follow-up at 15 months, study discontinuation for any reason, informed consent withdrawal or death; whichever comes first.

Table 6 Effectiveness

Variable	Definition	Timing
Date of death	Date of death	Post-index period
Tumour response	Assessment dates and categorical variable per IMWG response criteria (IMWG, 2021 Criteria) if feasible or to local standard practice: 
 • sCR • CR • VGPR • PR • No change/stable disease • PD 	Post-index period

Abbreviations: CR=complete response IMWG=International Myeloma Working Group; PD=Progressive disease; PR=partial response; sCR=stringent complete response; VGPR; very good partial response.

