8.7.2.3. Analysis of Key Secondary Objectives

For the key secondary objectives, the following will be described for the SP (overall and by line of treatment) during active treatment exposure periods:

- Average cycle dose (sum of all doses divided by total number of administrations per patient)
- Frequency and timing of ophthalmic monitoring relative to belantamab mafodotin administration for each cycle (type(s), number of examinations; overall and according to monitoring before and after the occurrence of ocular AESIs as well as treatment dose and frequency)
- Ocular AESIs in RRMM patients exposed to belantamab mafodotin occurring during the study period:
 - Number, proportions, co-occurrence and time to (specific) ocular AESIs; overall and by System Organ Class (SOC) and Preferred Term (PT) terms (MedDRA classification) and according to severity, grade, seriousness, action taken, duration, impact on daily living and relationship to treatment as well as treatment dose and frequency
 - Number, proportion, severity, grade, seriousness and duration of ocular AESIs by ophthalmic monitoring frequency, type(s) and timing relative to administration
 - Severity, grade, seriousness and duration of ocular AESIs by their treatment impact (e.g., dose changes, duration of interruptions/delays, discontinuation), use of artificial tears and dry eye comorbidity

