8.7.2.4. Analysis of Other Secondary Objectives

In addition, the following will be described for the SP (overall and by line of treatment):

- Exposure-adjusted incidence rate with 95% CI, overall and by SOC and PT names
 - Defined as the number of patients with at least one (specific) AE during follow-up divided by the sum of person-months at risk in the study.
 - Person-months at risk is defined as the duration of follow-up for patients without AEs plus the duration of follow-up until the date of the first (specific) AE for patients with an AE.
- Exposure-adjusted event rate with 95% CI, overall and by SOC and PT names
 - Defined as the number of (specific) AESIs during follow-up divided by the sum of person-months at risk in the study.
 - Person-months at risk is defined as the duration of follow-up.
- For patients with dose reductions, interruptions/delays or discontinuation of belantamab mafodotin treatment **due to an ocular AESI** during the study period, the following will be summarized (overall and by comorbidity, ocular AESI type and ocular AESI severity as well as treatment dose and frequency):
 - Number and proportions of patients
 - Primary reasons for dose reductions, interruptions/delays or discontinuation of treatment due to any AE
 - Belantamab mafodotin treatment patterns after occurrence of an ocular AESI (i.e., order of treatment changes and timing)

- Median, 95% CIs and 25th and 75th percentiles using the Kaplan-Meier (KM) method for time to dose reductions, interruptions/delays or discontinuation
- Duration of dose reductions and interruptions/delays or discontinuations
- Belantamab mafodotin treatment adherence, i.e., the total duration of treatment in days divided by the total follow-up time in days.
- Belantamab mafodotin treatment persistence, i.e., the proportion of patients still on treatment at specified time points, including 3-, 6-, 12- and 15-months of follow-up
- Treatment response (e.g., sCR, CR, VGPR or PR):
 - Best treatment response during follow-up
 - Treatment response at specified time points, including 12- and 15-months of follow-up
 - Proportion of patients with a maintained response (PR or better) at specific time points, including 12- and 15-months of follow-up
 - ORR with 95% CIs calculated based on the exact binomial distribution (Clopper-Pearson method)
- Median, 95% CIs and 25th and 75th percentiles using the KM method for:
 - OS (overall and based on response / non-response to treatment)

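### ORR and best response stay open to month 15 with no stop at progression or a new line, so responses to the next therapy count for belantamab mafodotin

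*Protocol*

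**What the plan says.** Four parts of the protocol fix the response window.

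- **Definition of ORR (8.3.1):** "ORR is defined as the proportion of patients with a best response (sCR, CR, VGPR or partial response [PR]) during the study period".
- **Definition of the study period (8.3.1):** it "spans from the time from the initial MM diagnosis until the end of follow-up at 15 months", or to study discontinuation, consent withdrawal or death if earlier. Progression, stopping the drug and a new line are not among the end points.
- **Collection (8.1):** "Safety and effectiveness data will be collected regardless of whether patients are on treatment or have discontinued treatment during follow-up". Section 8.3.6 describes "effectiveness data to be collected during the study period from the time of the first belantamab mafodotin dose", and Table 6 times tumour response to the whole post-index period.
- **Analysis (8.7.2.4):** "Best treatment response during follow-up", ORR with an exact binomial interval, response and maintained response at months 12 and 15, and OS and rwPFS split by response and non-response.

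Section 8.3.1 also defines DoR, from the first PR or better to the earliest PD or death. It defines a post-index treatment period too, which ends at the decision to discontinue permanently or at the "confirmed date of a new line of treatment or the date of the end of follow-up at 15 months", among other stops. ORR does not use that narrower period.

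**The concern.** Section 7.2 sets the objective as disease response to treatment. The derived outcome answers a different question: did the patient reach PR or better on anything within 15 months of the first dose?

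Take a patient who progresses at month 3, changes regimen, and reaches PR at month 8. Under the written definition:

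- the patient is a responder in ORR and in best response;
- if the PR persists, nothing in the text keeps the patient out of maintained response at month 12 or 15;
- the patient sits in the responder group for OS, having had to live long enough to receive and respond to another line, and in the responder group for rwPFS with an event at month 3;
- DoR starts at month 8 and ends at month 3.

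Section 8.9.1 says effectiveness results will be compared with clinical trial results, so an inflated ORR would carry into that comparison.

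**Working it through.** **1. The window, side by side**

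| Element | Start | Ends at progression? | Ends at discontinuation or new line? |
|---|---|---|---|
| Study period (ORR, 8.3.1) | MM diagnosis | No | No |
| Follow-up (best response, 8.7.2.4) | Index date | No | No |
| Tumour response collection (Table 6) | Index date | No | No |
| Post-index treatment period (8.3.1) | Index date | No | Yes |

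The three elements that govern response agree with each other, and none excludes an assessment made on a later regimen.

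**2. Direction.** Assessments on a later regimen can turn a non-responder into a responder. They cannot undo an earlier response, and the denominator does not change. The bias in ORR is therefore zero or positive.

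**3. DoR in the example.** First PR at month 8, earliest PD at month 3: 3 − 8 = −5 months.

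**4. How much time lies in the open part of the window.** Section 6.1 cites, for the pivotal study at the registration dose, ORR 32% of 97 (97.5% CI 21.7–43.6), median PFS 2.8 months and median OS 13.7 months. The ORR interval reproduces: 31/97 = 32.0%, exact 97.5% interval 21.7% to 43.6%. Assume exponential curves, S(t) = 2^(−t/median). The share alive after progression is then OS(t) − PFS(t):

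- month 6: 73.8% − 22.6% = 51.2%
- month 12: 54.5% − 5.1% = 49.4%
- month 15: 46.8% − 2.4% = 44.4%

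Roughly half the cohort would be alive after progression, with response still being collected, for much of the window.

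**5. Illustrative size.** Let r be the response rate to belantamab mafodotin, s the share of non-responders who start a next line within follow-up, and q the response rate to that line:

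ORR as defined = r + (1 − r) × s × q

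Take r = 0.32 from section 6.1. The protocol gives neither s nor q; the ranges below are assumptions.

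| s | q | ORR as defined | Excess |
|---|---|---|---|
| 20% | 10% | 0.32 + 0.68 × 0.2 × 0.1 = 33.4% | 1.4 points |
| 40% | 20% | 0.32 + 0.68 × 0.4 × 0.2 = 37.4% | 5.4 points |
| 60% | 30% | 0.32 + 0.68 × 0.6 × 0.3 = 44.2% | 12.2 points |

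At the planned 150 patients, 32% is 48/150 (exact 95% CI 24.6% to 40.1%). The middle row is about 56/150 (29.6% to 45.6%).

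**6. Can the window be closed with the data listed?** Only in part. Discontinuation has a decision date (8.3.1) and is captured in Table 3. The start of a new line is not a variable in Tables 2 to 7: Table 2 covers prior therapies, Table 3 collection stops at permanent discontinuation, and Table 6 holds only death and tumour response. The post-index treatment period therefore relies on a date that no table collects.

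**The case against.** The best defence is one of intent and weight. The objective speaks of response to treatment, so response to belantamab mafodotin is plainly meant. The study is descriptive, tests no hypothesis, and lists effectiveness last among the other secondary objectives. Section 8.7 leaves detailed methodology to the SAP, which is not shown and could restrict the window. A cut at discontinuation could largely be derived from the recorded decision date. At the low end of the assumptions the excess is 1.4 points, well inside an interval whose half-width at 48/150 is about 7.7 points.

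Much of this stands, and it limits the weight of the point. It does not remove it. The protocol does not leave the window to the SAP; it fixes one, so a SAP that closed it would depart from the stated definition. Sampling error also does not excuse a bias of known sign. A cut at discontinuation is too early for a response first documented after the last dose but before any new therapy.

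The text also invites stronger readings that the documents do not support:

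- **Responses to earlier lines count, because the study period starts at diagnosis.** Section 8.3.6 and Table 6 collect response only from the first dose. The start date is a wording slip with little numerical effect on ORR.
- **Ocular events before the first dose count.** Section 8.7.2.3 does refer to "Ocular AESIs in RRMM patients exposed to belantamab mafodotin occurring during the study period", and Table 7 ticks these events under the baseline period. But section 8.3.5 records events during or after administration, Table 5 times them to the index date and the post-index period, and the lead-in to 8.7.2.3 limits these analyses to active treatment exposure.
- **DoR runs on past progression.** It does not; it ends at the earliest PD. The defect is a negative duration for a next-line responder, not a prolonged one.
- **Most patients have about a year of follow-up after progression.** Death also ends follow-up. On the cited pivotal medians about 44–51% would be alive after progression at months 6 to 15. With the 7 to 10 month median OS cited elsewhere in section 6.1, only 2^(−15/7) = 23% to 2^(−15/10) = 35% would be alive at month 15.

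**Conclusion.** The point holds for the open end of the window. As written, ORR and best response credit next-line responses to belantamab mafodotin, the responder split of OS and rwPFS inherits the misclassification, and DoR can be negative. That ORR can only be biased upward follows from the definition and needs no assumption.

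The size does rest on assumptions. The range of 33.4% to 44.2% against 32% takes the pivotal-study ORR as the true rate, 20–60% next-line uptake among non-responders and 10–30% response to that line. It is an illustration, not a forecast. If few patients receive or respond to another line within follow-up, the excess is small.

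**What to change.** 1. In section 8.3.1, define best response and ORR on assessments from the index date to the earliest of first documented progression, start of a new anti-myeloma line, or end of follow-up.
2. Take DoR, maintained response and the responder and non-responder groups for OS and rwPFS only from responses in that window.
3. Align the ORR definition in 8.3.1, the effectiveness text in 8.3.6 with Table 6, and the response bullets in 8.7.2.4. Collection to month 15 can continue; only the assessments that count need limiting.
4. Add the start date of the next anti-myeloma line to the collected variables, for example in Table 6. The post-index treatment period needs it as well.
5. While editing, replace study period by post-index period where outcomes after the first dose are meant.

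The cost is definition wording, one eCRF date field and possibly a lower reported ORR. The date field is best added before data collection is far advanced, because later analysis wording cannot supply a date that was never collected.
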